4.2.2 Exclusion Criteria

Patients who meet any of the following exclusion criteria are not eligible to participate in this study:

- 1. Participation in another therapeutic clinical trial within 3 weeks of enrollment
- 2. A previous toxicity-related reaction to cancer therapy and have not recovered within 2 weeks of enrollment (>Grade 2 NCI-CTCAE Version 4.03)
- 3. Having received a major surgical operation within 4 weeks of enrollment or not completely recovered from a previous operation
- 4. Any serious or uncontrollable systemic disease, including but not limited to: Hypertension (after treatment, systolic blood pressure (SBP) > 180 mmHg and/or DBP > 100 mmHg) and active hemorrhagic disorders; patients who are determined by investigators as otherwise not suitable for participation in this study. Note: Patients that in the judgment of the investigator have clinical signs of disease progression during the screening period (i.e.: febrile neutropenia, ascites requiring drainage, hospitalization due to worsening underlying disease, etc.) will not be eligible for participation.
- 5. Active known infection, including hepatitis B, hepatitis C, and human immunodeficiency virus
- 6. Primary central nervous system (CNS) tumor or CNS metastases, as indicated by clinical symptoms, cerebral edema, and/or progressive growth (patients with a history of CNS metastases or cord compression are allowable if they have been definitively treated and have been clinically stable for at least 3 months, and off steroids or anticonvulsants ≥ 2 weeks before first dose of study drug)
- 7. Serious kidney injury, requiring dialysis
- 8. Serious liver injury, and advanced liver diseases of Child-Pugh class B and C

August 21, 2019 Confidential 42 / 74

 On medications that are strong CYP3A inhibitors or inducers unless patients are willing and able to change to use of an equivalent medication that is not a strong CYP3A inhibitor or inducer

- 10. Cardiac function and disease history which meets one or more of the following conditions:
 - Any risk which may increase QTc interval prolongation, such as hypokalemia, hereditary long QT syndrome, and taking drugs that can prolong QT interval
 - Acute myocardial infarction ≤ 6 months prior to Day 1
 - Clinically significant arrhythmia ≤ 6 months prior to Day 1
 - Congestive heart failure ≥ Grade 3 by New York Heart Association (NYHA)
 ≤ 6 months prior to Day 1
 - Cerebral vascular accident (CVA) \leq 6 months prior to Day 1
- 11. Are pregnant or breastfeeding

4.2.3 Patient Restriction

Patients should avoid grapefruit and products containing grapefruit.

4.2.4 Patient Completion and Discontinuation

4.2.4.1 Patient Completion

A patient will be considered complete if he/she has a valid PK profile and has not withdrawn from the study prior to completing the DLT assessment period (21 days from first dose of FN-1501).

4.2.4.2 Patient Discontinuation

A patient must be discontinued if any one or more of the conditions occur: 1) DLT occurs and the toxicity has not improved to Grade 1, Grade 0 or baseline within 14 days of onset; 2) occurrence of other toxicities that makes continuation of study treatment intolerable; 3) a third dose-reduction is required; 4) treatment delay is more than 4 weeks, unless resuming treatment is regarded beneficial to the patient by the investigator and agreed by Sponsor's medical monitor; 5) in the opinion of the investigator, continuous treatment is not beneficial to the patient.

A patient may voluntarily discontinue participation from this study at any time. If a patient is discontinued from participation in the study for any reason, the investigator must make every effort to perform the following evaluations 30 to 35 days from the last dose of FN-1501: physical examination, vital signs, ECG, laboratory tests (hematology, chemistry, coagulation, and urinalysis), and AE assessment. These data will be recorded as they comprise an essential evaluation that should be done prior to

August 21, 2019 Confidential 43 / 74

discharging any patient from the study. If a patient is discontinued from the study at any time due to an AE (as defined in Section 9.1), the procedures stated in Section 9.7 must be followed.

The reason for discontinuation will be recorded in the electronic case report form (eCRF). These reasons may include:

- Withdrawal of consent by the patient
- Discontinuation of FN-1501 by the sponsor
- Pregnancy
- Any significant AE that compromises the patient's ability to participate in the study
- The investigator or sponsor determines it is in the best interest of the patient
- Progression of disease at any time during the study
- Need for prohibited medication
- Lack of compliance with the study and/or study procedures (e.g., administration instructions, study visits)
- Significant deviation from the protocol without the consent of the sponsor

Premature discontinuation of FN-1501 occurs when a patient is discontinued for reasons other than unacceptable toxicity during DLT evaluation cycle. Prematurely discontinued patients will be considered for replacement after due consideration from sponsor and SMC.

5 Study Treatments

5.1 Description of Study Drug

The product is a white to off-white sparse cake or powder contained in vials. Each vial contains 10 mg FN-1501. It will be reconstructed with 5% glucose prior to use.

5.2 Dosage and Administration

Patients will receive intravenous infusion of FN-1501 on the assigned days starting with the 2.5 mg/day cohort. FN-1501 will be diluted in 10 mL of 5% glucose solution and added in 100 mL 5% glucose for intravenous infusion over 1 hour. For procedures for dose escalation, refer to Section 4.1.1.

August 21, 2019 Confidential 44 / 74

5.2.1 Dose Delays and Modifications

Interruption/reduction of dosing for AEs may take place any time during the study. Below are general guidelines for dose delays and modifications for FN-1501 related toxicities.

Dose Delays

Treatment with FN-1501 should be withheld from a patient who experiences an AE of Grade 3 or higher until the toxicity resolves to Grade 1, Grade 0 or baseline. Dosing with FN-1501 may be resumed following resolution of toxicity at the next lower dose level. The resumed dosing will be given at the next regularly scheduled time point. If the AE is clearly not associated with the study treatment, the dosing may be resumed at the original dose level, after discussion with the sponsor's medical monitor.

If a patient requires a treatment interruption of more than 4 weeks for any reason, the patient should be withdrawn from the study treatment, unless resuming the treatment is regarded beneficial to the patient by the investigator and agreed upon by the sponsor's medical monitor.

Dose Modifications

Dose reductions are allowed if patients resume study treatment after dose interruption for toxicity. A maximum of two dose reductions are permitted. If further dose reduction is needed, the patient should be withdrawn from study treatment.

A patient may switch to a higher dose at the discretion of the investigator, if 1) the safety of the higher dose level has been fully evaluated and determined not to exceed MTD; and 2) the patient has been treated at the current dose level for at least 2 cycles without experiencing a clinically significant treatment-emergent AE. However, if Grade 3 or higher toxicity occurs or continues after permitted dose increase or reduction, then the patient should be withdrawn from study treatment.

Any resumed or modified dose will start as a new cycle.

5.3 Precautions

Tumor Lysis Syndrome (TLS) has been reported as a potential risk in patients with AML, including those patients that have predisposing factors such as elevated lactate dehydrogenase, leukocytosis, tumor burden, hydration status and/or renal dysfunction.

Patients at risk of developing TLS or patients that develop TLS should be treated with prophylaxis and therapeutic measures respectively as per Institutional Guidelines.

August 21, 2019 Confidential 45 / 74

5.4 Treatment Assignment

Patients will be identified by a subject number. Each patient enrolled in this study will receive a unique subject number, which will be assigned when the patient is screened or enrolled in the study. Each patient receiving FN-1501 will also receive a treatment allocation number. Subject numbers and treatment numbers will be assigned in chronological order starting with the lowest number. Once a subject number and treatment number have been assigned to a patient, it cannot be reassigned to another patient.

A patient who withdraws from the study for reasons other than DLT may be replaced. If a patient is replaced, the replacement patient will be assigned the next available subject number and treatment number.

5.5 Drug Preparation

Specific instructions for acquisition, storage and preparation of FN-1501 and preparation of final dosing solution will be provided in the Pharmacy binder provided to the sites.

5.6 Packaging and Labeling

The drug product is packed in 10 mL, type I glass vials. The vial is sealed with a bromobutyl stopper covered by an aluminum flip-off cap.

The contents of the label will be in accordance with all applicable regulatory requirements.

5.7 Handling and Storage

The study drug will be dispatched to a study center only after receipt of the required documents in accordance with applicable regulatory requirements and the sponsor's procedures. Study drug must be dispensed or administered according to procedures described herein. Only patients enrolled in the study may receive study drug, in accordance with all applicable regulatory requirements. Only authorized study center personnel may supply or administer study drug. All study drugs must be stored in a secure area with access limited to the investigator and authorized study center personnel and under physical conditions that are consistent with study drug-specific requirements. The study drug must be stored as specified on the label and according to the latest version of the IB.

5.8 Product Accountability

The investigator is responsible for study drug accountability, reconciliation, and record maintenance. In accordance with all applicable regulatory requirements, the investigator or designated study center personnel must maintain study drug

August 21, 2019 Confidential 46 / 74

accountability records throughout the course of the study. This person(s) will document the amount of study drug received from the sponsor, the amount supplied and/or administered to and returned by patients, if applicable. After completion of the study, all unused product will be inventoried and packaged for return shipment by the hospital unit pharmacist. The inventoried supplies will be returned to the sponsor or destroyed on site after receiving written sponsor approval.

5.9 Assessment of Compliance

Patients will receive FN-1501 by intravenous infusion at the investigational site as outlined in the Study Assessment and Procedure Schedule (Table 2). All visits and treatment administrations will be recorded.

6 Concomitant Medications and Nondrug Therapies

6.1 Permitted Medications

All concomitant medications taken during the study will be recorded in the eCRF with indication, dose information, and dates of administration according to the Study Assessment and Procedure Schedule (Table 2). All prescription or non-prescription (over the counter) medications, as well as, vitamins, herbs and supplements taken, any special diets and alcohol use should be collected.

6.2 Prohibited Medications

Administration of all other anti-cancer therapy (cytotoxic, biologic, radiotherapy, or hormone therapy other than for replacement) while on treatment in this study is prohibited. Palliative radiotherapy for non-targeted lesions is permitted. Bisphosphonate use is permitted if the patient has already been on it for three or more months and on a stable dose. Corticosteroid courses of limited duration (2 weeks or less) are permitted, if used to treat a concomitant (non-cancer) medical condition.

During study treatment, drugs known to prolong the QT/QTc interval should be avoided unless there is no alternative treatment available, in accordance with ICH E14 [9]. If such a drug must be used, written approval from the sponsor's medical monitor is required. A list of drugs with QTc prolongation potential is presented in Table 4. A full list is provided through the Arizona Center for Education and Research on Therapeutics (CERT; "Drugs That Prolong the QT interval and/or Induce Torsades de Pointes"): Available at:

https://crediblemeds.org/index.php/tools/pdfdownload?f=cql en

August 21, 2019 Confidential 47 / 74

Table 4: Drugs with QTc prolongation potential

Antipsychotics	Type IA antiarrhythmics	Type IC antiarrhythmics	Class III antiarrhythmics
Chlorpromazine	Quinidine	Flecainide	Sotalol
Haloperidol	Procainamide	Encainide	Amiodarone
Droperidol	Disopyramide		
Quetiapine			
Olanzapine			
Amisulpride			
Thioridazine			
Tricyclic	Other	Antihistamines	Other
antidepressants	antidepressants		
Amitriptyline	Mianserin	Diphenhydramine	Chloroquine
Doxepin	Citalopram	Astemizole	Hydroxychloroquine
Imipramine	Escitalopram	Loratidine	Quinine
Nortriptyline	Venlafaxine	Terfanadine	Macrolides
Desipramine	Bupropion		Erythromycin
	Moclobemide		Clarithromycin

While the primary metabolic pathway for FN-1501 involves the CYP3A isoform, preliminary in vitro screening assays revealed that FN-1501 is not a strong inhibitor nor a strong inducer of human CYP isoenzymes tested. The use of drugs that are strong CYP3A4 inhibitors or inducers is prohibited (Table 5). Patients who require moderate CYP3A4 inhibitors during the study should be closely monitored. Please refer to http://medicine.iupui.edu/clinpharm/ddis/main-table/ for a complete list of CYP3A inhibitors.

Table 5: Prohibited Medications

Strong CYP3A inhibitors			
Indinavir	telithromycin	suboxone	nelfinavir
Itraconazole	ketoconazole	ritonavir	saquinavir
nefazodone clarithromycin			
Strong CYP3A inducers			
Carbamazepine	rifampicin	phenobarbital	phenytoin
St. John's wort			

Abbreviations: CYP = cytochrome P450

6.3 Other Medications to be Used with Caution

Gene expression data showed that FN-1501 is an inducer of CYP1A2 at the concentration of 0.100 μ M. FN-1501 also showed weak inhibition on CYP2C8 (IC₅₀: 38.8 μ M). Investigators should be aware that FN-1501 has the potential to interfere with the appropriate metabolism of medications that rely on these isoenzymes. Please refer to http://medicine.iupui.edu/clinpharm/ddis/main-table/ for the medication list.

7 Safety, Pharmacokinetic, Pharmacodynamic, and Other Assessments

A signed, written informed consent must be obtained prior to screening assessments and before any study-specific assessments are initiated. The study-specific assessments and procedures are shown in Table 2. The PK sampling, vital sign and ECG time points are presented in Table 2 and Table 3. Demographic and Baseline Assessments will include date of birth, race, height (in cm), body weight (in kg), and body mass index (BMI [in kg/m²]). For height and weight measurements, the patient will be allowed to wear indoor daytime clothing with no shoes. This data will be captured in the eCRF and database. After giving consent, patients will be required to undergo a medical screen to determine whether they are eligible to participate in the study according to the criteria listed in Section 4.2. Screening assessments will be completed within 21 days prior to the first dose of the study drug, except that radiological scans of tumor can be within 42 days prior to the first dose (Section 7.4).

Screening assessments completed within 72 hours of administration can be used as Day 1 of Cycle 1 assessments as indicated in Table 2. The screening assessments will include:

- Demographic data
- Medical history & baseline conditions
- Vital signs (SBP, DBP, pulse rate, temperature, and respiratory rate)
- Height and weight (BMI calculation)
- Complete physical exam
- ECOG performance status
- 12-lead ECG
- Review of concurrent medications
- CT or MRI
- Disease assessment for Solid Tumors or AML
- Pregnancy test for women of childbearing potential

August 21, 2019 Confidential 49 / 74

- Hematology
- Blood chemistry plus serum amylase and lipase tests
- Bone marrow biopsy for related assessments for patients with AML (see Section 7.4)
- Coagulation test
- Urinalysis
- Recording of AEs and SAEs

The above-mentioned data will be captured in the source documents and entered into the eCRF. All tests will be done by local laboratories. Any results falling outside the normal range will be repeated at the discretion of the investigator.

7.1 Assessments During the Treatment Period

Routine safety assessments include vital signs, weight, physical exam, and AE assessment will be performed at every visit. Other safety assessments include 12-lead ECG, bloodwork, disease assessments, bone marrow biopsy for related assessments for patients with AML, and urinalysis will be performed as indicated in Table 2.

7.1.1 Local Laboratory Evaluation

Laboratory assessments will be performed at a local certified laboratory at the time points specified in Table 2. Laboratory assessments need not be repeated on Day 1 if these assessments were completed for screening within 72 hours prior to the first administration. Required laboratory assessments are listed in Table 6.

August 21, 2019 Confidential 50 / 74

Table 6: Clinical laboratory assessments

Blood Chemistry	Hematology	Coagulation	Urinalysis (dipstick)
Alkaline phosphatase	Full and differential	Prothrombin time	Appearance
Alanine	blood count	Partial thromboplastin	рН
aminotransferase	Red blood cell count	time	Specific
Aspartate	Hematocrit		gravity
aminotransferase	Hemoglobin		Glucose
Albumin	Mean corpuscular		Protein
Bicarbonate	hemoglobin		Ketones
Electrolytes (Ca, K,	Mean corpuscular		Blood cells
Na, Cl, P)	hemoglobin		Blood cells
Creatinine	concentration		
Glucose	Mean corpuscular volume		
Lactate dehydrogenase	Platelet counts		
Magnesium Phosphorus	White blood cell count with differential		
Serum amylase*	Neutrophil count		
Serum lipase*	_		
Total protein			
Total bilirubin			
Urea			

Abbreviations: Ca = calcium; Cl = chloride; K = potassium; Na = sodium

Laboratory results should be assessed by the Investigator. In the event of neutropenia (ANC $<1000/\text{mm}^3$), thrombocytopenia (platelets $<50,000/\text{mm}^3$), or Grade 3 clinical chemistry toxicity, the relevant assessments will be conducted as frequently as the Principal Investigator feels is needed until toxicity resolves to \le Grade 2. If warranted, additional testing can also be done, or the relevant tests done more frequently in accordance with institutional guidelines. All patients who have any Grade 3 or Grade 4 laboratory abnormalities at withdrawal from the study must be followed up until they have returned to Grade 1 or Grade 2, unless these are not likely

August 21, 2019 Confidential 51 / 74

^{*} These tests will be conducted together with blood chemistry.

to improve due to the underlying disease. On routine urinalysis, if urine protein is $\geq 2+$ by dipstick, then 24-hour urine for total protein and a random urine sample for total protein and creatinine will be obtained. If urine protein is > 2 g/24 hours, study drug administration will be interrupted until it returns to ≤ 2 g/24 hours. If urine protein is ≤ 2 g/24 hours, further clinical evaluation and/or more frequent testing may be performed as clinically indicated. A random urine protein to creatinine ratio can serve as a reliable surrogate for the 24-hour urine protein when following patients with urine protein of ≤ 2 g, documented by a 24-hour urine collection. In such cases, the 24-hour urine for total protein should be repeated only if a clinically significant increase is observed in the random urine protein to creatinine ratio. After week 9, this test will be performed as clinically indicated.

7.1.2 Physical Examination and Vital Signs

A complete or targeted physical examination, vital signs (SBP, DBP, pulse rate, temperature, and respiratory rate), and weight examination will be performed at the time points specified in Table 2.

Complete physical examination includes assessments of cardiovascular, respiratory, abdominal and neurological systems as well as lymph nodes/spleen, skin, oropharynx and extremities. Targeted physical examinations should be limited to systems of clinical relevance (i.e., cardiovascular, respiratory, lymph nodes, liver, and spleen), and those systems associated with clinical signs/symptoms.

7.1.3 Electrocardiogram

A 12-lead ECG will be performed in triplicate at Screening, on Cycle 1, Day 1, Cycle 2, Day 1. Thereafter, triplicate is only if clinically indicated (i.e., prolonged QTc interval) as detailed in Table 2. ECGs will be performed on the days specified in Table 2 and time points specified in Table 3. Other ECGs may be performed as clinically indicated. Patients should be in the supine position for at least 10 minutes prior to having ECGs performed and remain in that position for the duration of the test.

Patients with significant QTc prolongation to undergo 12-lead ECG as detailed in Table 2. Significant QTc prolongation will be defined as an interval > 500 msec; an interval which increases by ≥ 60 msec over baseline, and/or decreased by 50 msec below pre-dose recording. The ECG tracing should be examined and interpreted by a trained physician.

If prolongation of QT or QT interval corrected for heart rate (QTc) is noted during the first 2 weeks, triplicate 12 lead ECGs will be conducted weekly during Cycle 2, and then once every 3 weeks before administration and 5-15 minutes after administration

August 21, 2019 Confidential 52 / 74

on Day 1 of every cycle from Cycle 3 onwards, until discontinuation of FN-1501 treatment.

If a patient has significant QTc prolongation:

- He/she will suspend study drug administration
- The patient will be medically assessed, treated appropriately, and closely followed (ECGs at least three times per week) until the QT and QTc interval return to within 30 msec of baseline
- The medical monitor will be consulted prior to administering further doses or re-challenging
- The medical monitor will be consulted prior to administering higher doses

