- 7. Have discontinued all previous cancer therapies for at least 21 days (for solid tumors) or at least 7 days (for AML) or 5 half-lives prior to study treatment, whichever is shorter, and recovered from the acute adverse effects of therapy
- 8. Expected to survive at least 2 to 3 months
- 9. Left ventricular ejection fraction (LVEF) ≥ 50% and QTc interval < 450 ms
- 10. Women shall meet either of the following conditions before enrollment
 - Infertile (see Section 4.2.1)
 - For those of childbearing potential, they should have a negative serum pregnancy test during the screening, agree to refrain from lactation, and use effective contraception such as hormonal methods associated with inhibition of ovulation, condom, intra-uterine device, surgical sterilization (including partner's vasectomy) or sexual abstinence during the study and for 30 days after the last administration of study drug
- 11. Men who are engaging or plan to engage in sexual activity with a female of childbearing potential must either have a prior vasectomy or agree to use effective contraception such as condoms, sexual abstinence, or appropriate methods taken by their partner(s) during the study and for 90 days after the last dose

August 21, 2019 Confidential 14 / 74

12. Patients must have adequate organ functions as indicated by the following screening laboratory values:

- Serum total bilirubin ≤ 1.5 × upper limit normal (ULN) (Serum total bilirubin can be ≤ 3.0 × ULN if patients have hemolysis or congenital hemolytic diseases)
- Creatinine < 1.5 × ULN or estimated creatinine clearance ≥ 50 mL/min
- Aspartate aminotransferase (AST) and alanine aminotransferase (ALT) ≤ 2.5 × ULN (AST and ALT can be ≤5 × ULN for patient with liver metastases)
- Absolute neutrophil count (ANC) $\geq 1.5 \times 10^9/L$
- Platelets $\geq 100 \times 10^9/L$
- Hemoglobin ≥ 9 g/dL or ≥ 5.6 mmol/L (Note: Criteria must be met without a transfusion within 2 weeks of obtaining the sample)

Note: Laboratory requirements for complete blood counts (hemoglobin, ANC, and platelets) do not apply to AML patients

Exclusion criteria:

Patients who meet any of the following exclusion criteria are not eligible to participate in this study:

- 1. Participation in another therapeutic clinical trial within 3 weeks of enrollment

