- 3. Disease assessment every 6 weeks to coincide with every other cycle. Refer to Section 7.4 for details.
- 4. These assessments should be conducted, and the results should be available before study drug administration in each cycle. If assessments are conducted within 3 days prior to Day 1 of the cycle, the data can be recorded as Day 1 data of the cycle. See Table 3 for details. Height to be measured at Screening for BMI calculation.
- 5. A full physical exam will be conducted at screening, on Day 1 of each cycle and at follow-up. A full physical exam includes assessments of cardiovascular, respiratory, abdominal and neurological systems as well as lymph nodes/spleen, skin, oropharynx and extremities. Refer to Section 7.1.2 for details.

August 21, 2019 Confidential 37 / 74

6. ECGs to be performed prior to that days dose (if applicable) and after the patient has been supine for at least 10 minutes and should be performed with the patient in the same physical position for the duration of the test. ECG at Screening: performed in triplicate (5-10 min between readings). ECG at Day 1 of Cycle 1: performed in triplicate (5-10 min between readings) at the days indicated in Table 2 and time points and time windows detailed in Table 3. Cycle 2 Day 1: Perform in triplicate (5-10 min between readings) only if patient has a significant QTc prolongation, that is, a) > 500 msec; or b) increased by ≥ 60 msec over baseline; and/or c) decreased by 50 msec below pre-dose recording. If prolongation of QT or QT interval corrected for heart rate (QTc) is noted during the first 2 weeks, triplicate 12 lead ECGs will be conducted weekly during Cycle 2, and then once every 3 weeks before administration and 5-15 minutes after administration on Day 1 of every cycle from Cycle 3 onwards, until discontinuation of FN-1501 treatment. Refer to Section 7.1.3 for details on significant QTc prolongation.

- 7. Data obtained up to 42 days prior to Day 1 is acceptable.
- 8. Only in women of childbearing potential and additionally at the investigator's discretion.
- 9. In the event of neutropenia, thrombocytopenia, or \geq Grade 3 clinical chemistry toxicity, these assessments will be conducted as frequent as the investigator feels necessary until toxicity is resolved (\leq Grade 2). Refer to Table 6 for details on laboratory assessments.

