- 10. Bone marrow biopsy for related assessments will be performed in patients with AML at Screening, every 6 weeks to coincide with the end of every other cycle, and at the end of the study or at time of relapse. Based on the patient's clinical condition, complete blood counts or bone marrow assessments may occur more frequently based on Investigator's judgment.
- 11. If urine protein is $\geq 2+$ by dipstick, then 24-hour urine for total protein and a random urine for total protein and creatinine will be collected and evaluated. See Section 7.1.1 for details.
- 12. Refer to Table 3 for details. PK sample must be collected pre-dose on Day 3 of Cycle 1 and pre-dose on Day 1 of Cycle 2 and as detailed in Table 3.
- 13. The investigational drug should be administered at approximately same time each time. The investigational drug is administered on Days 1, 3, 5, 8, 10, and 12 of each 21-day cycle. Not all treatment administration days are illustrated in the table.

August 21, 2019 Confidential 38 / 74

Table 3: Sampling Schedule (Day 1 of Cycle 1 to Day 1 of Cycle 2 Only; Refer to Table 2 for complete schedule)

Cycle		Cycle 1							Cycle 2				
Day of cycle		Day 1						Day 2	Day 3	Day 1			
		Post-Day 1 Dose Time Point:											
Time point ¹	Pre- dose	5 min	15 min	30 min	1 hr	2 hr	4 hr	6 hr	8 hr	12 hr	24 hr	48 hr (pre-Day 3 dose)	Pre-dose
PK sample	X	X	X	X	X	X	X	X	X	X	X	X ¹	X ¹
ECG ²	X				X	X							X
Vital signs ²	X	X	X	X	X	X	X	X	X	X	X	X	X

^{1.} Abbreviations: ECG = electrocardiogram; hr = hour; min = minute; PK = Pharmacokinetic Time point relative to end of infusion on Cycle 1, Day 1. Blood sample will be collected pre-dose on Day 3 of Cycle 1 and Day 1 of Cycle 2. See next page for sampling time windows.

2. Vital signs and ECG also collected at follow-up not shown (see Table 2 for details). Vital signs and ECG are predose unless otherwise indicated.

August 21, 2019 Confidential 39 / 74

Sampling Time Windows

The following time windows (relative to end of infusion) are allowed for PK sampling, ECG, and vital signs, as applicable:

• For pre-dose time points (Days 1, 3, and Cycle 2, Day 1): within 1 hr before dosing the planned study drug administration

• For 24 hr and 48 hr time points: +/- 1 hr., (prior to dosing on Day 3)

• For 2, 4, 6, 8 and 12 hr time points: +/- 30 min.

• For 30 min, 1 hr time points: +/- 15 min.

• For 15 min time point: +/- 5 min.

• For 5 min time point: +/- 3 min.

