4.2 Selection of Study Population

4.2.1 Inclusion Criteria

Each patient must meet all the inclusion criteria for this study at the time of starting study treatment:

- 1. Male and female 18 years old and above
- 2. Able to understand and sign informed consent form
- Patients with histologically or cytologically confirmed advanced solid tumors
 who have relapsed or refractory disease or relapsed/refractory AML for which no
 standard therapies expected to produce clinical benefit to the patient are available
- 4. Patients with diagnosed solid tumors must have at least one lesion that is measurable per RECIST v1.1 criteria
- Patients with relapsed or refractory AML must be diagnosed with AML based on World Health Organization (WHO) criteria (≥ 20% blasts in bone marrow)
 Patients with acute promyelocytic leukemia are excluded.
- 6. Eastern Cooperative Oncology Group (ECOG) Performance Status 0 or 1
- 7. Have discontinued all previous cancer therapies for at least 21 days (for solid tumors) or at least 7 days (for AML) or 5 half-lives prior to study treatment, whichever is shorter, and recovered from the acute adverse effects of therapy
- 8. Expected to survive at least 2 to 3 months
- 9. Left ventricular ejection fraction (LVEF) \geq 50% and QTc interval \leq 450 ms
- 10. Women shall meet either of the following conditions before enrollment
 - Infertile, defined as having a bilateral oophorectomy (ovariectomy), or a bilateral tubal ligation, or being post-menopausal for at least 1 year
 - For those of childbearing potential, they should have a negative serum pregnancy test during screening, agree to refrain from lactation, and use effective contraception such as hormonal methods associated with inhibition of ovulation, condom, intra-uterine device, surgical sterilization (including partner's vasectomy) or sexual abstinence during the study and 30 days after the last administration of study drug
- 11. Men who are engaging or plan to engage in sexual activity with a female of childbearing potential must either have a prior vasectomy or agree to use effective contraception such as condoms, sexual abstinence and appropriate methods taken by their partner(s) during the study and 90 days after the last dose

August 21, 2019 Confidential 41 / 74

- 12. Patients must have adequate organ functions as indicated by the following screening laboratory values:

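### The definition of significant QTc prolongation includes a 50 msec QTc decrease, so a shortening alone suspends study drug

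*Protocol*

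**What the plan says.** Section 7.1.3 (Electrocardiogram) gives three limbs for significant QTc prolongation: an interval above 500 msec; an increase of at least 60 msec over baseline; "and/or decreased by 50 msec below pre-dose recording". Table 2 footnote 6 has the same list in lettered form, ending "and/or c) decreased by 50 msec below pre-dose recording". The Amendment 4 rationale says that section 7.1.3 was updated to match the Table 2 footnotes, so both places are current text.

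Section 7.1.3 attaches actions to the defined term without qualification:

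- "He/she will suspend study drug administration"
- After assessment and treatment, follow-up is set as "closely followed (ECGs at least three times per week) until the QT and QTc interval return to within 30 msec of baseline"
- No further dose, re-challenge or higher dose may be given until the medical monitor has been consulted.

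In footnote 6 the term also decides whether the Cycle 2 Day 1 ECG is done in triplicate.

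The entry limit is "QTc interval < 450 ms" in the Synopsis (inclusion criterion 9) and at most 450 ms in section 4.2.1. Section 4.2.1 fixes the time at which it applies: "Each patient must meet all the inclusion criteria for this study at the time of starting study treatment".

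**The concern.** The first two limbs describe prolongation. The third describes the opposite, yet by its connector it meets the definition without either of the others. No text confines it to patients who also meet limb a or b, and none treats shortening as a category of its own. Read literally, a patient whose QTc only fell must be taken off drug under the heading of prolongation.

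Three details make the limb harder to apply. It has no inequality sign, so it is unclear whether exactly 50 msec or at least 50 msec is meant. It is measured from the pre-dose recording, whereas limb b and the recovery target are measured from baseline. It does not say which pre-dose recording counts once the patient is past Cycle 1 Day 1.

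At stake are unneeded dose holds in a first-in-human escalation study, and a safety rule whose intent the investigator has to guess.

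**Working it through.** The plan has no figure of its own to reproduce here. The check applies the definition to readings and then uses the plan's limits to bound where limb c can operate. I read limb c as a fall of 50 msec or more.

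**Inputs**
- Limb a: QTc > 500 msec (7.1.3; Table 2 footnote 6)
- Limb b: QTc − baseline ≥ 60 msec (same places)
- Limb c: pre-dose QTc − QTc ≥ 50 msec (same places)
- Entry limit: 450 msec at the start of treatment (Synopsis; 4.2.1)
- Assumed readings, not in the protocol: those in the table and in steps 4 and 5

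**1. The definition applied** (assumed baseline = pre-dose = 440 msec)

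| Post-dose QTc | a: > 500 | b: change ≥ +60 | c: fall ≥ 50 | As written | Limbs a and b only |
|---|---|---|---|---|---|
| 390 | no | no (−50) | yes (440 − 390 = 50) | suspend | no action |
| 500 | no | yes (+60) | no | suspend | suspend |

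The fall to 390 msec suspends drug although the reading is 500 − 390 = 110 msec below limb a.

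**2. Bound on Cycle 1 Day 1.** If the pre-dose recording respects the entry limit, the highest reading that meets limb c is 450 − 50 = 400 msec (just under 400 with the strict limit in the Synopsis). That is at least 500 − 400 = 100 msec below limb a and at least 450 − 400 = 50 msec inside the entry limit.

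**3. What limb c adds as written.** A reading that meets limb c together with a or b is already caught by a or b. The readings caught only by limb c have fallen at least 50 msec from pre-dose and are neither above 500 msec nor 60 msec over baseline. As written, removing limb c loses no detection of prolongation.

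**4. The two reference points.** Suppose baseline is 420 msec, a later-cycle pre-dose reading is 470 msec and the same-day post-dose reading is 420 msec. Pre-dose is +50 on baseline, below limb b. The post-dose reading is 470 − 420 = 50 msec below pre-dose, so limb c is met. It also equals baseline, so the recovery target of 30 msec is met at the moment drug is suspended.

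**5. If the direction word is wrong.** The different reference point leaves open that an increase over pre-dose was intended. Suppose baseline is 430, pre-dose 420 and post-dose 470 msec. The change is +50 on pre-dose but only +40 on baseline, and 470 is below 500. Limbs a and b miss this reading, whereas a limb reversed to an increase would catch it. Deletion without asking would then drop an intended trigger.

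**The case against.** The strongest reply is that only the name is wrong. A first-in-human protocol may reasonably pause drug for a 50 msec swing in either direction. Every listed action suits a shortening too, and the recovery target of 30 msec is two-sided. This largely stands: the protocol does not state that intent, but it does not exclude it, and the actions need not change if shortening is to be acted on.

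It can also be said that the limb has few scheduled chances to operate. For a patient not already flagged, Table 3 has post-dose ECGs only at 1 and 2 hours on Cycle 1 Day 1, and the Cycle 2 Day 1 ECG is pre-dose. Post-dose ECGs from Cycle 3 are required only if prolongation was noted in the first two weeks. This stands if the limb refers to the same day's pre-dose recording, which the text leaves open.

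A reader might infer two stronger things, and the documents support neither.

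- **That the mislabel distorts the safety results or the DLT count.** Section 10.3 lists and summarises measured ECG values and changes from baseline, so a fall appears as a fall. Nothing requires the label to be recorded or analysed as a category. The DLT definitions in section 4.1.1 do not use the term.
- **That a held patient is under-dosed yet counts toward a cohort.** The dosing rule is: "The investigational drug is administered on Days 1, 3, 5, 8, 10, and 12 of each 21-day cycle". So 6 − 1 = 5 Cycle 1 doses follow the Day 1 ECGs, and the completion rule in section 4.2.4.1 names no minimum number of doses. But the number missed could be anything from 0 to 5, depending on when the medical monitor is consulted. That range covers every outcome and shows no actual harm.

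**Conclusion.** The concern holds in this form: in two current places the protocol makes a 50 msec QTc decrease sufficient for significant QTc prolongation, and section 7.1.3 attaches mandatory suspension, intensified ECGs and medical monitor consultation to that term. On Cycle 1 Day 1 the patients caught by this limb have a QTc of about 400 msec or less.

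The 400 msec bound rests on the pre-dose recording meeting the entry limit and on reading the limb as 50 msec or more. The 440 to 390 msec example is assumed. The error is cautious for the individual patient, its frequency cannot be estimated from the protocol, and no effect on DLT counts, dose decisions or QTc summaries is shown. It is a rule that is wrong as written and cheap to correct. It is not a threat to the trial's conclusions.

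**What to change.** In section 7.1.3 and Table 2 footnote 6, restrict significant QTc prolongation to a QTc above 500 msec or an increase of at least 60 msec over baseline. Before limb c is removed, have the sponsor confirm what it was meant to say:

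- **If shortening was meant:** move it to a separately named QTc shortening criterion, for which the existing actions may be kept, or delete it.
- **If an increase over pre-dose was meant:** correct the direction and keep it as a prolongation limb.

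If the limb is kept in either form, add the inequality and say which pre-dose recording is the reference.

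The cost is wording in two places, one query to the sponsor and, if a shortening criterion is kept, a short management line in section 7.1.3. Design and data collection do not change.
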